3.4. Mechanistic Endpoints

The following *mechanistic endpoints* will be assessed:

1. Incidence and kinetics of DSA and autoantibodies, specifically Collagen V (ColV) and k-alpha-1 tubulin ($\kappa\alpha 1T$);
2. Frequency, kinetics, phenotype and function of peripheral B cells;
3. Frequency, kinetics and cytokine profiles of allo- and auto reactive T cells;
4. Incidence and quantity of B cells and B cell proximity to other cells in the graft tissue.

3.5. Stratification, Randomization, and Blinding/Masking

This is a double-blinded study; therefore, medication assignments will be blinded to the study participants as well as to the site clinical personnel. **Only the site research pharmacist will have access to the unblinded randomization schedule for that site.** In the event the subject undergoes a life-threatening reaction, then study subject and treating physician will be unblinded to the treatment assignment. In the event the subject undergoes repeat severe infusion or hypersensitivity reactions, despite appropriate treatment, then study subject and treating physician will be unblinded to the treatment assignment. IND safety reports will be reported to the FDA, DSMB, and IRBs in an unblinded fashion.

Randomization treatment assignments will be developed by the SACCC statisticians and stored on the SACCC server. The SACCC will maintain a central web-based randomization system. Once the subject is determined to be eligible based on the criteria, the site personnel will be provided the appropriate treatment assignment.

3.5.1 Procedure for Unblinding/Unmasking

Unblinding must be approved by the study Medical Monitor unless an immediate life threatening condition has developed and the Medical Monitor is not accessible. The site investigator will notify the protocol chair(s) and the study Statistical and Clinical Coordinating Center team of the unblinding event on the next business day. The emergency unblinding will also be reported to the Data and Safety Monitoring Board (DSMB).

A full account of the event will be recorded on the Study Treatment Unblinding eCRF, including the date and time of the unblinding, the reason for the decision to unblind, and the name of the individual who made the decision and the names of the Medical Monitor and others who were notified. The reasons for unblinding of a participant's treatment will be included in the final study report.

Unblinding the study due to an approved interim analysis, final analysis, or study termination will require written approval from NIAID.

4. Selection of Participants and Clinical Sites

4.1. Rationale for Study Population

Although early outcomes in pediatric transplantation have improved in the past 2 decades, conditional survival beyond the early post-transplant period has not improved significantly, due primarily to the development of chronic allograft dysfunction. This is particularly evident for pediatric lung transplant recipients. In recent years, accumulating evidence has implicated antibodies as an important contributor to chronic allograft dysfunction. These include antibodies to donor histocompatibility antigens or cryptic self-antigens exposed during organ transplantation or subsequent graft injury. The mechanistic connection between antibody development and chronic allograft dysfunction in lung transplantation has yet to be determined. Moreover, effective therapies for prevention and management of pathologic antibodies for chronic allograft dysfunction have yet to be developed.

This study and the associated mechanistic studies will dissect the role B cells play in this process, including direct antibody mediated effects and indirect effects on cellular alloimmune and autoimmune response.

4.2. Enrollment Inclusion Criteria

Individuals who meet all of the following criteria are eligible for enrollment as study participants:

1. Subject and/or parent guardian must be able to understand and provide informed consent;
2. Less than or equal to 21 years of age;
3. Candidate for a primary lung transplant (listed for lung transplant);
4. Adequate bone marrow function based on the following criteria:
 - a. ANC: >1000/mm³
 - b. Platelets: >100,000/mm³
 - c. Hemoglobin: >7 gm/dL
 - d. AST or ALT < 2x Upper Limit of Normal unless related to primary disease
5. Female and male subjects with reproductive potential must agree to use FDA approved methods of birth control for 12-months after completion of treatment.

4.3. Enrollment Exclusion Criteria

Individuals who meet any of these criteria are not eligible for enrollment as study participants:

1. Inability or unwillingness of a participant to give written informed consent or comply with study protocol;
2. Multi-organ transplant;
3. Previous treatment with rituximab (Rituxan®);
4. History of severe allergic anaphylactic reactions to humanized or murine monoclonal antibodies;
5. History of severe reaction to previous therapy with IVIG;
6. History of Burkholderia cenocepacia;
7. History of anti-CD20 therapy;
8. Persistent hypogammaglobulinemia (IgG < lower level of normal for age based on local laboratory ranges or 400 gm/dL for >2 months) and/or IVIG replacement therapy;
9. Positive blood culture, sepsis or other disease process with hemodynamic instability at time of enrollment;

10. Any history of serologic positivity to HIV, HBsAg, HbCAb and HCV Ab;
11. History of malignancy less than 2 years in remission of malignancy (any history of adequately treated in-situ cervical carcinoma, or adequately treated basal or squamous cell carcinoma of the skin will be permitted);
12. Any condition, including psychiatric disorders, that in the opinion of the investigator would interfere with the subject's ability to comply with study requirements;
13. Participation in another investigational trial within 4 weeks of enrollment;
14. Currently lactating or plans to become pregnant during the timeframe of the study follow-up period;
15. Past or current medical problems or findings from physical examination or laboratory testing that are not listed above, which, in the opinion of the investigator, may pose additional risks from participation in the study, may interfere with the participant's ability to comply with study requirements or that may impact the quality or interpretation of the data obtained from the study.

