	
of adequately treated in-situ cervical carcinoma, or adequately treated basal or squamous cell carcinoma of the skin will be permitted);
 
12. Any condition, including psychiatric disorders, that in the opinion of the investigator would interfere with the subject's ability to comply with study requirements;
 
13. Participation in another investigational trial within 4 weeks of enrollment;
 
14. Currently lactating or plans to become pregnant during the timeframe of the study follow-up period;
 
15. Past or current medical problems or findings from physical examination or laboratory testing that are not listed above, which, in the opinion of the investigator, may pose additional risks from participation in the study, may interfere with the participant's ability to comply with study requirements or that may impact the quality or interpretation of the data obtained from the study.

Randomization Inclusion Criteria	
1. Serum IgG immunoglobulin level greater than lower level of normal for age based on local laboratory ranges or 400 mg/dL within 90 days prior to randomization;
 
2. Female subjects of childbearing potential must have a negative pregnancy test within 48 hours of transplant;
 
3. Negative for Hepatitis B infection (if at time of transplant, subject does not exhibit effective immunization, the subject should be re-tested).

Randomization Exclusion Criteria	
1. Use of an induction agent other than Thymoglobulin®;
 
2. Renal insufficiency requiring hemodialysis or ultrafiltration;
 
3. Inability to obtain intravenous access;
 
4. Positive blood culture, sepsis or other disease process with hemodynamic instability at time of transplant;
 
5. Use of investigational agent(s) within 5 half-lives of the investigational drug or 4 weeks, whichever is longer;
 
6. Receipt of a MMR vaccine within 30 days prior to randomization;
 
7. Any condition that, in the opinion of the investigator, would interfere with the subject's ability to comply with study requirements.

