4.4. Randomization Inclusion Criteria

Individuals who meet all of the following criteria are eligible for randomization:

1. Serum IgG immunoglobulin level greater than lower level of normal for age based on local laboratory ranges or 400 gm/dL within 90 days prior to randomization;
2. Female subjects of childbearing potential must have a negative pregnancy test within 48 hours of transplant;
3. Negative for Hepatitis B infection (if at time of transplant, participant does not exhibit effective immunization, the participant should be re-tested).

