7.4. Treatment for Hypogammaglobulinemia

Intravenous immune globulin will be administered at 400-500 mg/kg every four weeks to patients who develop hypogammaglobulinemia (IgG less than lower level of normal for age based on local laboratory ranges or 400 mg/dL) following transplant. For subjects with severe hypogammaglobulinemia (IgG less than 200 mg/dL), an IV loading dose of 1 gram/kg will be administered. The maintenance IV dose of 400-500 mg/dL at four week intervals will be titrated to response. IgG trough levels will be measured prior to an infusion.

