	
 g. Magnitude of change in standard deviation of tacrolimus levels following intervention 
2. Post-transplant safety outcomes including:
 
 a. Incidence and severity of infection episodes b. Serious adverse events related to rituximab
Secondary Mechanistic Endpoints	
 1. Incidence and kinetics of DSA and autoantibodies, specifically Collagen V (ColV) and k-alpha-1 tubulin (kα1T) 2. Frequency, kinetics, phenotype and function of peripheral B cells 3. Frequency, kinetics and cytokine profiles of allo- and auto reactive T cells 4. Incidence and quantity of B cells and B cell proximity to other cells in the graft tissue
Accrual Objective	50 randomized pediatric lung transplant recipients
Study Duration	
4.5 years (3.5 year accrual + 1-4.5 year follow-up period)
 
All participants will be followed for a minimum of 1 year post-transplant. Participants will continue follow-up visits (up to 4.5 years post-transplant) until the last participant completes 1 year of follow-up.

Enrollment Inclusion Criteria	
 1. Subject and/or parent/guardian must be able to understand and provide informed consent 2. Less than or equal to 21 years of age 3. Candidate for primary lung transplant (listed for lung transplant) 4. Female and male subjects with reproductive potential must agree to use FDA approved methods of birth control for 12 months after completion of treatment 5. Adequate bone marrow function based on the following criteria: 
 a. ANC > 1000mm³ b. Platelets > 100,000/mm³ c. Hemoglobin > 7 g/dL d. AST or ALT <2x Upper Limit of Normal unless related to primary disease
Enrollment Exclusion Criteria	
 1. Inability or unwillingness of a participant to give written informed consent or comply with study protocol 2. Multi-organ transplant 3. Previous treatment with rituximab (Rituxan®) 4. History of severe allergic anaphylactic reactions to humanized or murine monoclonal antibodies 5. History of severe reaction to previous therapy with IVIG 6. History of Burkholderia cenocepacia 7. History of anti-CD20 therapy

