	
 8. Persistent hypogammaglobulinemia (IgG < lower level of normal for age based on local laboratory ranges or 400 g/dL for >2 months) and/or IVIG replacement therapy 9. Positive blood culture, sepsis or other disease process with hemodynamic instability at time of enrollment 10. Any history of serologic positivity to HIV, HBsAg, HBcAb and HCV Ab 11. History of malignancy less than 2 years in remission of malignancy (any history of adequately treated in-situ cervical carcinoma, or adequately treated basal or squamous cell carcinoma of the skin will be permitted) 12. Any condition, including psychiatric disorders, that in the opinion of the investigator would interfere with the subject's ability to comply with study requirements 13. Participation in another investigational trial within 4 weeks of enrollment 14. Currently lactating or plans to become pregnant during the timeframe of the study follow-up period 15. Past or current medical problems or findings from physical examination or laboratory testing that are not listed above, which, in the opinion of the investigator, may pose additional risks from participation in the study, may interfere with the participant's ability to comply with study requirements or that may impact the quality or interpretation of the data obtained from the study

Randomization Inclusion Criteria
	
 1. Serum IgG immunoglobulin level greater than lower level of normal for age based on local laboratory ranges or 400 mg/dL within 90 days prior to randomization 2. Female subjects of childbearing potential must have a negative pregnancy test within 48 hours of transplant 3. Negative for Hepatitis B infection (if at time of transplant, subject does not exhibit effective immunization, the subject should be re-tested)

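### Unit errors: the IgG limit of 400 is printed in grams per dL in two eligibility criteria, and Section 7.4 prints the IVIG maintenance dose as a concentration

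*Protocol*

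**What the plan says.** Exclusion 8 in Protocol Section 4.3 bars candidates with persistent hypogammaglobulinemia. It defines this as IgG below the local lower limit of normal for age, or below "400 gm/dL for >2 months". The Protocol synopsis prints the same figure and unit for this exclusion, and the SAP synopsis has "400 g/dL for >2 months".

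Randomization inclusion 1 asks for IgG above the local age-based limit or above a fixed value. Protocol Section 4.4 prints the fixed value as "400 gm/dL within 90 days prior to randomization". The Protocol synopsis and the SAP synopsis both give this criterion as "400 mg/dL within 90 days prior to randomization".

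Section 7.4 defines post-transplant hypogammaglobulinemia as "IgG less than lower level of normal for age based on local laboratory ranges or 400 mg/dL" and, for the severe form, states "severe hypogammaglobulinemia (IgG less than 200 mg/dL), an IV loading dose of 1 gram/kg will be administered". The same paragraph gives the IVIG dose twice: first as 400-500 mg/kg every four weeks, then, as the maintenance dose at the same interval, as 400-500 mg/dL.

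**The concern.** One limit appears in two units that differ by a factor of 1000, and the protocol contradicts itself on a single criterion: randomization inclusion 1 is in mg/dL in the synopsis and in gm/dL in Section 4.4. Sections 4.3 and 4.4 are the operative eligibility text. Section 15.1 permits no deviations, so a site should not have to guess a threshold. All three versions of exclusion 8 carry the gram unit, so the correct unit for that criterion has to be inferred from a different criterion or section.

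The IVIG slip is of another kind. An amount per dL cannot be given as a dose, and the sentence after it concerns IgG trough levels, so a reader could take 400-500 mg/dL for a trough target.

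**Working it through.** No calculation in the plan is being reproduced. The check sets the printings side by side and converts units.

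**The IgG limit of 400**

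| Place | Criterion | Unit printed |
|---|---|---|
| Protocol synopsis | Enrollment exclusion 8 | gm/dL |
| Protocol Section 4.3 | Enrollment exclusion 8 | gm/dL |
| SAP synopsis | Enrollment exclusion 8 | g/dL |
| Protocol Section 4.4 | Randomization inclusion 1 | gm/dL |
| Protocol synopsis | Randomization inclusion 1 | mg/dL |
| SAP synopsis | Randomization inclusion 1 | mg/dL |
| Protocol Section 7.4 | Definition of hypogammaglobulinemia | mg/dL |

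Grams: 4. Milligrams: 3. Total: 4 + 3 = 7.

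**Is gm a local shorthand for milligrams?** No. The Protocol glossary lists gm as gram and mg as milligram. The enrollment criteria use the gram unit correctly for another analyte: "Hemoglobin: >7 gm/dL" in Protocol Section 4.2 and "Hemoglobin > 7 g/dL" in the SAP synopsis. A PDF-reading fault is also unlikely, because the gram unit occurs in four places, in two spellings and in both documents.

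**Conversion**

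- 400 g/dL × 1000 mg/g = 400,000 mg/dL.
- 400,000 / 400 = 1000 times the limit as printed in mg/dL.
- 400,000 / 200 = 2000 times the severe limit in Section 7.4.
- 400 g/dL × 10 dL/L = 4,000 g/L, that is, 4 kg of IgG in a litre of serum, which is not possible.

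**Literal effect on each criterion**

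- Exclusion 8: the limbs are joined by *or*, so meeting either is enough. Every candidate's IgG has been below 400 g/dL for more than two months, so the gram limb captures everyone.
- Section 4.4: the limbs are again joined by *or*, but this is an inclusion. Nobody can exceed 400 g/dL, so the gram limb drops out and the age-based limb decides alone. Candidates can still qualify through it.

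**The IVIG dose in Section 7.4.** The two statements share the figures (400-500) and the interval (four weeks). The second calls the quantity an IV dose, and the loading dose between them is per kg of body weight. The second unit should therefore be mg/kg. One of the two printings is wrong.

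**The case against.** The strongest reply is that these are typographical slips that the documents themselves resolve. Both synopses carry mg/dL for the criterion misprinted in Section 4.4, Section 7.4 defines the same condition at 400 mg/dL, and the correct IVIG dose opens the paragraph that contains the wrong one. Since 400 g/dL is physically impossible, no site would apply it. All of that stands, and it is why the point is minor.

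A second reply is that exclusion 8 is headed by the term persistent hypogammaglobulinemia, so a candidate with normal IgG is not caught. A clinician would read it that way. But the parenthesis is what defines the term, so as written the gram limb does capture every candidate.

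Three smaller points also have merit. Only Sections 4.3 and 4.4 are operative eligibility text; the other two gram printings are in synopses. The eligibility limit and the IVIG dose are separate slips that share only the type of error. Finally, other units need checking: the recipient schedule in Protocol Appendix 1 prints the study drug as 375 mg/kg, whereas Protocol Sections 3.1 and 6.1.1.2 and SAP Section 6.2 give 375 mg/m². That is a separate error in the investigational dose. It does not make the items here any less wrong.

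**Conclusion.** The concern holds, as a minor correction. The IgG limit is overstated by a factor of 1000 in 4 of its 7 printings, including both operative eligibility sections, and 1 of the 2 printings of the 400-500 IVIG dose has a unit that cannot describe a dose. The age-based limb of each eligibility criterion is unaffected.

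The conclusion rests on the printed units, the glossary and the mg/dL and mg/kg values elsewhere in the documents; no outside figure is needed. That sites would in practice infer the intended units is a judgement, though a safe one. Endpoints, sample size, power and analyses do not depend on any of these values.

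**What to change.** Print the IgG limit as 400 mg/dL in four places: enrollment exclusion 8 in the Protocol synopsis, in Protocol Section 4.3 and in the SAP synopsis, and randomization inclusion 1 in Protocol Section 4.4. Print the maintenance IVIG dose in Protocol Section 7.4 as 400-500 mg/kg.

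That is 4 + 1 = 5 unit corrections, four in the Protocol and one in the SAP. Design, sample size and analysis do not change. The Protocol changes need IRB approval before they are implemented (Section 16.1), so they are best carried in the next amendment, together with the study drug unit in Appendix 1.

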4.4. Randomization Inclusion Criteria

Individuals who meet all of the following criteria are eligible for randomization:

1. Serum IgG immunoglobulin level greater than lower level of normal for age based on local laboratory ranges or 400 gm/dL within 90 days prior to randomization;
2. Female subjects of childbearing potential must have a negative pregnancy test within 48 hours of transplant;
3. Negative for Hepatitis B infection (if at time of transplant, participant does not exhibit effective immunization, the participant should be re-tested).

4.5. Randomization Exclusion Criteria

Individuals who meet any of these criteria are not eligible for randomization:

1. Use of an induction agent other than Thymoglobulin®;
2. Renal insufficiency requiring hemodialysis or ultrafiltration;
3. Inability to obtain intravenous access;
4. Positive blood culture, sepsis or other disease process with hemodynamic instability at time of transplant;
5. Use of investigational agent(s) within 5 half-lives of the investigational drug or 4 weeks, whichever is longer;
6. Receipt of a MMR vaccine within 30 days prior to randomization;
7. Any condition that, in the opinion of the investigator, would interfere with the subject's ability to comply with study requirements.

4.6. Selection of Clinical Sites

The target population for this study consists of pediatric lung transplant recipients. Subjects will be enrolled at sites throughout the United States. The sites participating in the study have performed the majority of pediatric lung transplants annually in the United States. The target population therefore is a fair representation of the pediatric lung population.

5. Known and Potential Risks and Benefits to Participants

5.1. Risks of rituximab (Rituxan®)

No dose-limiting effects were observed in Phase I/II studies. Reported adverse events including fever, chills, headache, nausea, vomiting, rhinitis, asthenia, and hypotension, occurred primarily during rituximab infusions and typically responded to an interruption of the infusion and resumption at a slower rate.

Fatal Infusion Reactions: Severe and fatal cardiopulmonary events, including angioedema, hypoxia, pulmonary infiltrates, acute respiratory distress syndrome, myocardial infarction, and cardiogenic shock, have been reported. These severe reactions typically occurred during the first infusion with time to onset of 30-120 minutes.

Cardiac Events: Patients with preexisting cardiac conditions, including arrhythmia and angina, have had recurrences of these cardiac events during rituximab infusions.

Tumor Lysis Syndrome: Tumor lysis syndrome, some with fatal outcome, has been reported and is characterized in patients with a high number of circulating malignant cells ($\geq 25,000$ ul) by rapid reduction in tumor volume, renal insufficiency, hyperkalemia, hypocalcemia, hyperuricemia, and hyperphosphatemia.

Renal Events: Rituximab has been associated with severe renal toxicity including acute renal failure requiring dialysis, and in some cases has led to death. Renal toxicity has occurred in patients with high numbers of circulating malignant cells ($\geq 25,000/\text{mm}^2$) or high tumor burden who experience tumor lysis syndrome and in patients administered concomitant cisplatin.

Mucocutaneous Reactions: Severe bullous skin reactions, including fatal cases of toxic epidermal necrolysis and paraneoplastic pemphigus, have been reported in patients treated with rituximab. The onset of reaction has varied from 1 to 13 weeks following rituximab exposure.

Nervous System:

a. Posterior reversible encephalopathy syndrome (PRES)/Reversible Posterior Leukoencephalopathy Syndrome (RPLS): Cases of posterior reversible encephalopathy syndrome (PRES)/reversible posterior leukoencephalopathy syndrome (RPLS) have been reported. Signs and symptoms include visual disturbance, headache, seizures and altered mental status, with or without associated hypertension. A diagnosis of PRES/RPLS requires confirmation by brain imaging. The reported cases had recognized risk factors for PRES/RPLS, including hypertension, immunosuppressive therapy and/or other concomitant therapies.

b. Progressive multifocal leukoencephalopathy (PML): PML is a rare disease caused by the reactivation of latent JC virus in the brain. Immunosuppression allows reactivation of the JC virus which causes demyelination and destruction of oligodendrocytes resulting in death or severe disability. Rare cases of PML, some resulting in death, have been reported in patients with hematologic malignancies who have received rituximab. The majority of these patients had received rituximab in combination with chemotherapy or as part of a hematopoietic stem cell transplant. Cases of PML resulting in death have also been reported following the use of rituximab for the treatment of autoimmune diseases. The reported cases had multiple risk factors for PML, including the underlying disease and long-term immunosuppressive therapy or chemotherapy. Most cases of PML were diagnosed within 12 months of their last infusion of rituximab.

Physicians should consider PML in any patient presenting with new onset neurologic manifestations. Consultation with a neurologist, brain MRI, and lumbar puncture should be considered as clinically indicated. In patients who develop PML, rituximab should be discontinued and reductions or discontinuation of any concomitant chemotherapy or immunosuppressive therapy should be considered.

Hematologic Events: In clinical trials, Grade 3 and 4 cytopenias were reported in 48% of patients treated with rituximab; these include: lymphopenia (40%), neutropenia (6%), leukopenia (4%), anemia (3%), and thrombocytopenia (2%). The median duration of lymphopenia was 14 days (range, 1 to 588 days) and of neutropenia was 13 days (range, 2 to 116 days). A single occurrence of transient aplastic anemia (pure red cell aplasia) and two occurrences of hemolytic anemia following Rituximab therapy were reported.

In addition, there have been a limited number of postmarketing reports of prolonged pancytopenia, marrow hypoplasia, and late onset neutropenia.

Infectious Events: Rituxan® induced B cell depletion in 70% to 80% of patients with NHL and was associated with decreased serum immunoglobulins in a minority of patients; the lymphopenia lasted a median of 14 days (range, 1-588 days). Infectious events occurred in 31% of patients: 19% of patients had bacterial infections, 10% had viral infections, 1% had fungal infections, and 6% were unknown infections. Serious infectious events (Grade 3 or 4), including sepsis, occurred in 2% of patients.

Hepatitis B Reactivation: Hepatitis B virus (HBV) reactivation with fulminant hepatitis, hepatic failure, and death has been reported in some patients with hematologic malignancies treated with rituximab. The majority of patients received rituximab in combination with chemotherapy. The median time to the diagnosis of hepatitis was approximately four months after the initiation of rituximab and approximately one month after the last dose.

Participants with pre-existing Hepatitis B infection will not be eligible to participate in this study.

Other Serious Viral Infections: The following additional serious viral infections, either new, reactivated or exacerbated, have been identified in clinical studies or postmarketing reports. The majority of patients received Rituxan® in combination with chemotherapy or as part of a hematopoietic stem cell transplant. These viral infections included JC virus (progressive multifocal leukoencephalopathy [PML]), cytomegalovirus, herpes simplex virus, parvovirus B19, varicella zoster virus, West Nile virus, and hepatitis C. In some cases, the viral infections occurred up to one year following discontinuation of Rituxan® and have resulted in death.

Bowel Obstruction and Perforation: Abdominal pain, bowel obstruction and perforation, in some cases leading to death, were observed in patients receiving Rituxan® in combination with chemotherapy for DLBCL. In post-marketing reports, which include both patients with low-grade or follicular NHL and DLBCL, the mean time to onset of symptoms was 6 days (range 1–77) in patients with documented gastro-intestinal perforation. Complaints of abdominal pain, especially early in the course of treatment, should prompt a thorough diagnostic evaluation and appropriate treatment.

Immunogenicity: Patients may develop a human anti-chimeric antibody (HACA) response with rituximab treatment. The clinical significance of this is unclear.

Pregnancy: B cell lymphocytopenia generally lasting less than 6 months can occur in infants exposed to rituximab in utero.

Immunization: Response rates may be reduced with non-live vaccines.

Additional Safety Signals: The following serious adverse events have been reported to occur in patients following completion of rituximab infusions: arthritis, disorders of blood vessels (vasculitis, serum sickness and lupus-like syndrome), eye disorders (uveitis and optic neuritis), lung disorders including pleuritis and scarring of the lung (bronchiolitis obliterans), that may result in fatal outcomes, and fatal cardiac failure.

See the rituximab Investigator Brochure for additional details regarding safety experience with rituximab.

